1.3 Exploratory Objectives

- 1.3.1 Identify predictive patterns of blood biomarkers which identify patients at high-risk of developing clinically significant osteonecrosis.
- 1.3.2 Identify MRI findings during late induction which correlate with osteonecrosis lesions seen during reinduction.
- 1.3.3 Identify patterns of diurnal blood pressure variation as measured by ambulatory blood pressure monitoring associated with the later development of osteonecrosis.
- 1.3.4 Compare induction blood pressure control and intervention arm to echocardiographic changes at reinduction II.
- 1.3.5 Evaluate patient-reported, health-related quality of life in patients during induction and after 1.5 years of therapy when many experience the symptoms of osteonecrosis.

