5.0 REQUIRED EVALUATIONS, TESTS, AND OBSERVATIONS

5.1 Pre-Study Evaluations

All entry/eligibility studies must be performed within 10 days prior to entry onto the trial (unless otherwise specified). Evaluations performed as part of TOT17 evaluation and therapy should be used when feasible to avoid duplicate studies.

Evaluation— must be obtained before enrollment	Within 10 days prior to enrollment
History and physical exam with height (cm), weight (kg), and BSA	X
Diagnosis of acute lymphoblastic leukemia/ lymphoma (ALL)	X
Laboratory studies: CBC with Diff, Chem 18, Urinalysis, PT, PTT	X
Echocardiogram	X
Pregnancy test for females of childbearing potential	X

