5.2 Evaluations during Therapy

Evaluation	Timing during Induction	Timing post-Induction
Ambulatory blood pressure monitoring (ABPM)	Once for 12-30 hours on day 4-7, once for 12-30 hours on day 23-28	-
Magnetic resonance imaging of hip and knee	Once during Days 23-28#	Reinduction 2 per Total 17 protocol
Vasomotor testing (arterial elasticity, pulse wave velocity) #	Once during Days 23-28	Once between Early Intensification day 57 and Consolidation day 28, (optional) once Continuation week 120 ±2 weeks
Serum for vascular biomarkers ^{&}	Day 22 +/- 2 days	Week 17 of Continuation (Reinduction II)
Echocardiogram		Once during week 17-19 of Continuation (Reinduction II)#
Symptom survey (PROMIS: Ped 25 Profile, Pain interference 8a, Physical activity 8a, Mobility 8a)	Once on day 23-28	Week 17 of Continuation (Reinduction II) ± 2 weeks, week 49 ± 3 weeks
Semi-structured interview of treatment and symptom burden #		Week 49 ± 3 weeks (with symptom survey)

All days/ weeks refer to the date of Total 17 therapy (i.e. day 22 refers to day 22 of Total 17, not the 22nd day since HYPERION entry or randomization).

***The St. Jude IRB requires that a female patient of childbearing potential must have a negative pregnancy test as a condition of clinical research eligibility.*

SJCRH Memphis patients only

& See HYPERION Manual of Operations for collection, processing and shipping instructions.

Obtain other studies as needed for good patient care and per the TOT17 protocol.

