5.6 Modifications for Collaborating Sites

All sites will complete ambulatory blood pressure monitoring, Reinduction 2 MRI evaluations, serum vascular biomarkers, and symptom surveys for all patients. Vasomotor testing, echocardiography at week 17, and patient interviews will be performed only at St. Jude. Induction MRI may be performed at collaborating sites based on scanner design and sequence availability. Induction MRI may be performed at collaborating sites based on scanner design and sequence availability.

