6.0 EVALUATION CRITERIA

6.1 Response Criteria

All patients will be evaluated clinically and radiographically for the development of osteonecrosis. Patients with radiographic (MRI or plain film x-ray) findings of osteonecrosis will be assessed for symptoms by the treating physician or designee. CTCAE version 4 criteria will be used to categorize the severity of osteonecrosis. MRI imaging will be centrally reviewed by a radiologist blinded to treatment assignment to assess the involvement of epiphyseal surfaces (0, <30%, ≥30%) which will be determined for each effected joint.

Blood pressures for each patient will be documented in the research database as the median of each week during induction and the median of each post-induction phase.

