10.6 Exploratory Objectives

Identify predictive patterns of blood biomarkers which identify patients at high-risk of developing clinically significant osteonecrosis.

Associations between the blood biomarkers and CTCAE grade 2 or higher ON will be analyzed using mixed-effect logistic regression models.

Identify MRI findings during late induction which correlate with osteonecrosis lesions seen during reinduction.

The MRI finding during late induction is represented by a 3-level ordinal variable (none, small, large). The ON lesions seen during reinduction are represented by a binary variable (large, less than large). The association will be tested by the Chi-square test on a 3-by-2 contingency table with ordered rows.

Compare induction blood pressure control and intervention arm to echocardiographic changes at reinduction II.

Echocardiographic changes at reinduction II is measured by the LV strain which is a continuous variable. Comparison of the LV strain between the intensive BP treatment and standard care arms will be performed by Wilcoxon rank-sum test.

Evaluate patient-reported, health-related quality of life in patients during induction and after 1.5 years of therapy when many experience the symptoms of osteonecrosis.

Survey response scores will be summarized by descriptive statistics including mean, standard deviation, minimum, maximum, quartiles, range and inter-quartile range.

Time frame: The analysis will begin within 6 months after the MRI assessments of the last randomized patient is completed, except for the last exploratory objective for which the analysis will begin within 6 months after the last randomized patient is followed for 1.5 years after completion of chemotherapy.

Responsible investigators: [name], [name]

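### Exploratory objective 1.3.4 names induction blood pressure control, but section 10.6 gives it no analysis and leaves the pre-enrolment echocardiogram unused

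*Combined protocol and SAP*

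**What the plan says.** Section 1.3 gives objective 1.3.4 as "Compare induction blood pressure control and intervention arm to echocardiographic changes at reinduction II". Section 10.6 repeats it and then supplies the whole analysis in two sentences: "Echocardiographic changes at reinduction II is measured by the LV strain", which it calls continuous, and "Comparison of the LV strain between the intensive BP treatment and standard care arms will be performed by Wilcoxon rank-sum test".

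The related provisions are:

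- **Pre-enrolment scan.** Section 5.1 says "All entry/eligibility studies must be performed within 10 days prior to entry onto the trial" unless otherwise specified, and its table marks an echocardiogram as required. It does not name LV strain for that scan.
- **On-study scan.** Section 5.2 schedules one echocardiogram, "Once during week 17-19 of Continuation (Reinduction II"), for Memphis patients, and none during induction. Section 5.6 confirms the site limit: "Vasomotor testing, echocardiography at week 17, and patient interviews will be performed only at St. Jude".
- **Blood pressure data.** Section 6.1 says "Blood pressures for each patient will be documented in the research database as the median of each week during induction".
- **Summary table.** Section 10.8 titles the analysis for 1.3.4 as echocardiographic change against induction blood pressure. It lists 80 participants and gives Reinduction II as the only data collection time frame.

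**The concern.** The objective asks two questions, and the analysis addresses one. A team that follows section 10.6 exactly will report whether strain differs by arm. It will say nothing about whether pressure during induction is related to strain, which is the relation that the section 10.8 title announces. If the gap is filled later, the pressure summary, the covariates and the model will all be chosen with the data in hand.

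A second, lesser gap is that the objective speaks of changes while the analysis names no earlier value, difference or adjustment. An echocardiogram from before randomisation is required of every patient, and nothing in the plan uses it.

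**Working it through.** **1. Objective against analysis.** The documents state no power, alpha, effect size or standard deviation for this objective, only the 80 participants, so there is no figure to reproduce. The check is a comparison of texts.

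| Element of objective 1.3.4 | Data provided for | Analysis in section 10.6 |
|---|---|---|
| Intervention arm | Randomisation (10.2) | Wilcoxon rank-sum on LV strain |
| Induction blood pressure control | Weekly induction medians (6.1) | None |
| Echocardiographic changes | Pre-enrolment scan (5.1) and week 17-19 scan (5.2) | LV strain; no baseline value named |

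The second row is empty, and no other section fills it. The provision for regression models in section 10.2 concerns the primary and secondary objectives when factors are unbalanced between arms, so it does not reach this one.

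**2. Is the pre-enrolment scan a proper covariate?** It is due within 10 days before entry, and randomisation takes place on day 4 of induction (Protocol Summary). The scan therefore precedes assignment and cannot be affected by it. What remains unknown is whether strain is read on it.

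**3. What would baseline adjustment buy in the arm comparison?** This is an illustration on assumptions that are not in the documents: the 80 patients split 40 per arm, two-sided 5%, 80% power, normal data, equal SD at both scans, and baseline strain available for all. Rho is the correlation between baseline and week 17-19 strain.

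- Follow-up only, t test: sqrt(2/40) x (1.960 + 0.842) = 0.626 SD.
- Follow-up only, Wilcoxon: 0.626 / sqrt(0.955) = 0.641 SD.
- Baseline-adjusted (ANCOVA): 0.626 x sqrt(1 - rho^2).
- Simple change score: 0.626 x sqrt(2(1 - rho)).

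| rho (assumed) | Planned Wilcoxon | ANCOVA | Change score |
|---|---|---|---|
| 0.3 | 0.64 | 0.60 | 0.74 |
| 0.5 | 0.64 | 0.54 | 0.63 |
| 0.7 | 0.64 | 0.45 | 0.49 |

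At rho = 0.3 the gain is slight, and part of it (0.641 to 0.626) comes from leaving the rank test under assumed normality, not from the baseline. With 35 per arm the planned test detects 0.69 SD, and ANCOVA 0.64, 0.58 and 0.48 SD. A simple change score is no better than follow-up alone until rho exceeds about 0.5, so ANCOVA is the form to prefer.

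**The case against.** The best defence concerns the baseline. A reader might infer that the arm comparison is biased, or that the plan plainly fails to measure what it set out to measure. The documents support neither inference. The arms are randomised, so a follow-up-only Wilcoxon test is a valid test of the arm effect. The wording is also ambiguous: the objective speaks of changes at reinduction II, not from baseline to it. Section 2.3 uses the same expression for findings in hypertensive patients without describing a baseline comparison. Section 10.8 lists a single time frame, whereas rows that draw on several time points list them. On that reading, schedule and analysis agree on one comparison at one time. The opposite reading, that change in strain was intended, is also open.

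A reader might further assume that every patient has a baseline strain value, or that adjustment is worth a definite number of extra patients. Section 5.1 promises only an echocardiogram. The documents give no correlation, and one assumed for strain against strain would not carry over if some other baseline measure were substituted.

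All of this stands, and it reduces the baseline point to a matter of precision and clear wording. It does not touch the other half: randomisation does not supply a missing analysis of induction blood pressure.

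**Conclusion.** The concern holds in two parts of unequal strength.

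- **Induction blood pressure.** The objective and the summary table both name it, the data are collected, and no analysis is specified. This follows from the text alone and needs no assumption.
- **Baseline echocardiogram.** A required pre-randomisation scan goes unused. The cost is precision, not validity. Its size is unknown from the documents; on the assumptions above, the detectable difference would fall from about 0.64 SD to between 0.60 SD (rho 0.3) and 0.45 SD (rho 0.7), provided strain can be read at baseline.

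The importance is low. The objective is exploratory and confined to Memphis patients, and nothing here bears on the primary analysis.

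**What to change.** 1. **Add the missing analysis.** In section 10.6, specify a regression of week 17-19 LV strain on a defined summary of the weekly induction median systolic pressures, for example their mean. Adjust for age and sex, because the pressure targets in section 4.1 depend on them, and for baseline strain where available. State in advance whether arm is also in the model, since pressure after day 4 is partly a result of arm. Report the result as an observational association, because achieved pressure is not randomised.
2. **Settle the baseline.** State whether LV strain is, or can be, read from the pre-enrolment echocardiogram. If so, replace the Wilcoxon test by ANCOVA, or rank ANCOVA if normality is doubtful, of week 17-19 strain on arm adjusted for baseline strain, and add the pre-enrolment scan to the section 10.8 time frame. If not, keep the planned test and describe its result as a level at reinduction II, not a change.
3. **Say how missing baseline strain is handled.** A missing-value indicator is defensible in the randomised arm comparison. In the blood pressure regression it can introduce bias, so use complete cases or imputation there.

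The cost is a few lines of text, one more model, and extraction of strain from scans already required. No new visit or test is needed. The main risk is that baseline strain is missing for some patients or cannot be recovered.

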10.7 Anticipated Completion Dates

Anticipated primary completion date: 3/2023

Anticipated study completion date: 3/2025

10.8 Summary of Primary and Secondary Objectives

Objective#	Objective Type	Analysis#	Resp Party	Stat	Safety	Analysis Measure	Analysis Title	Data Collection Time Frame	# of Participants
1.1.1	P	1	SEK	CC	N	Patient	Intensive vs. conventional hypertension control effect on osteonecrosis	Time on therapy	160
1.2.1	S	2	SEK	CC	N	Patient/ Joint	Antihypertensive intervention patients over time	Time on therapy/ Reinduction II	160
1.2.2	S	3	SCK/CM	CC	N	Patient/ Joint	Antihypertensive treated patients vs. historic control	Time on therapy/ Reinduction II	160
1.2.3	S	4	ND	CC	N	Patient	Blood pressure achieved by intervention arm	Through reinduction II	160
1.2.4	S	5	CM	CC	N	Patient	Induction MRI	Induction	80
1.2.4	S	6	DM	CC	N	Patient	Vascular function by vasomotor testing	Induction, consolidation, off therapy	80
1.2.4	S	7	SEK	CC	N	Patient	Blood markers of vascular dysfunction	Induction, reinduction II	160
1.3.1	E	7	SEK	CC	N	Patient	Blood markers of osteonecrosis risk	Induction, reinduction II	160
1.3.2	E	3/5	SCK/CM	CC	N	Patient	Early vs late MRI findings of osteonecrosis	Induction, Reinduction	80
1.3.3	E	8	ND	CC	N	Patient	ABPM blood pressures vs osteonecrosis	Induction	160
1.3.4	E	7	GB	CC	N	Patient	Echo changes at reinduction vs induction blood pressure	Reinduction II	80
1.3.5	E	9	EK	CC	N	Patient	HRQoL and symptom survey	Induction, reinduction II, week 49	160
1.3.5	E	10	EK	NA	N	Patient	Narrative symptom description	Week 49	80

11.0 OBTAINING INFORMED CONSENT

11.1 Consent at Enrollment

The process of informed consent for HYPERION will follow institutional policy. The informed consent process is an ongoing one that begins at the time of enrollment and ends after the completion of therapy. Informed consent should be obtained by the attending physician or his/her designee, in the presence of at least one non-physician witness.

Throughout the entire treatment period, participants and their parents receive constant education from health professionals at St. Jude and are encouraged to ask questions regarding alternatives and therapy. All families have ready access to chaplains, psychologists, social workers, and the St. Jude ombudsperson for support, in addition to that provided by the primary physician and other clinicians involved in their care.

We will also obtain verbal assent from children 7 to 14 years old and written assent for all participants ≥ 14 years of age

11.2 Consent at Age of Majority

The age of majority in the state of Tennessee is 18 years old. Research participants must be consented at the next clinic visit after their 18th birthday. If an affiliate or collaborating site is located in a country or state where a different age of majority applies, that location must consent the participants according to their local laws.

11.3 Consent When English is Not the Primary Language

When English is not the patient, parent, or legally authorized representative's primary language, the Social Work department will determine the need for an interpreter. This information documented in the participant's medical record. Either a certified interpreter or the telephone interpreter's service will be used to translate the consent information. The process for obtaining an interpreter and for the appropriate use of an interpreter is outlined on the Interpreter Services, OHSP, and CTO websites. Collaborating sites should follow institutional policy.

APPENDIX I: PERFORMANCE STATUS CRITERIA

PERFORMANCE STATUS CRITERIA					
Karnofsky and Lansky performance scores are intended to be multiples of 10					
ECOG (Zubrod)		Karnofsky		Lansky	
Score	Description	Score	Description	Score	Description
0	Fully active, able to carry on all pre-disease performance without restriction	100	Normal, no complaints, no evidence of disease	100	Fully active, normal
		90	Able to carry on normal activity, minor signs or symptoms of disease	90	Minor restrictions in physically strenuous activity
1	Restricted in physically strenuous activity by ambulatory and able to carry out work of a light or sedentary nature, e.g., light housework, office work	80	Normal activity with effort; some signs or symptoms of disease	80	Active, but tires more quickly
		70	Cares for self; unable to carry on normal activity or do active work	70	Both greater restriction of and less time spent in play activity
2	Ambulatory and capable of self-care but unable to carry out any work activities; up and about more than 50% of waking hours	60	Requires occasional assistance, but is able to care for most of his/her needs	60	Up and around, but minimal active play; keeps busy with quieter activities
		50	Requires considerable assistance and frequent medical care	50	Gets dressed, but lies around much of the day; no active play, able to participate in all quiet play and activities
3	Capable of only limited self-care, confined to bed or chair more than 50% of waking hours	40	Disabled, requires special care and assistance	40	Mostly in bed; participates in quiet activities
		30	Severely disabled, hospitalization indicated; death not imminent	30	In bed; needs assistance even for quiet play
4	Completely disabled; cannot carry on any self-care; totally confined to bed or chair	20	Very sick, hospitalization indicated. Death not imminent	20	Often sleeping; play entirely limited to very passive activities
		10	Moribund, fatal processes progressing rapidly	10	No play; does not get out of bed
